## 1. Project Summary

We plan a randomized clinical trial comparing four user-friendly, non-invasive topical pain treatments, including a novel thermomechanical distraction technique, for breast cancer patients undergoing radiotracer injection for sentinel lymph node mapping. There is significant variability in how practices approach minimizing pain with radiotracer injection. Patients have identified this procedure as particularly painful out of all the procedures they undergo related to breast cancer treatment. To date, no best practice approach has been identified that is easily implemented into clinical workflows across practice types. Our objective is to identify a practical and widely adoptable solution to this persistent problem and improve the experience of breast cancer patients starting their treatment trajectory within the health system.

## 2. Significance

Each year, over 270,000 American women will be diagnosed with breast cancer, making it the most common non-cutaneous malignancy in this population (1). The majority of these women have localized disease and will undergo sentinel lymph node (SLN) biopsy for cancer staging, as the presence of axillary lymph node metastasis is one of the most important prognostic factors for early stage breast cancer. Unfortunately, preoperative radiotracer injection for axillary SLN mapping can be extremely painful for some breast cancer patients, the pain of which is often severely underestimated by physicians (2). Indeed, radiotracer injection has been identified by some patients as the most painful experience in the operative day including surgery itself (3). The field of breast surgery has made large strides in improving patient experiences of breast surgery, including improving localization methods for breast conservation and incorporating regional blocks for the operative procedure. However, the pain with preoperative radiotracer injection remains distressing for patients. In order to enhance the experience of already anxious patients facing breast surgery, it is imperative that we identify methods to optimize pain control. Patient experience is an important component of the overall quality of health care and is essential for building positive relationships between patients and providers (4). These experiences and relationships are especially critical for breast cancer patients who are often only starting their treatment trajectory within the healthcare system.

## 3. Background

**3.1 Periareolar radiotracer injection is the preferred method for SLN identification in breast cancer patients (5) but is extremely painful.** In current practice, there is wide variability on pain management for radiotracer injection with no clear gold-standard. Intraoperative injection after initiation of surgical anesthesia would likely minimize pain the most. However, although some centers have successfully incorporated intraoperative injection of radiotracer into clinical flow (6–8), there are significant implementation challenges with this approach, including constraints associated with handling of radioactive material and coordination with nuclear medicine staff. For most centers, pre-operative injection is a necessity (8).

**3.2 Prior studies have demonstrated that the injection of local anesthetic such as lidocaine significantly reduces pain associated with subsequent or concomitant radiotracer injection (9–11) but may also reduce success of lymphatic mapping (Table).** While the reduction in pain scores with lidocaine injection is encouraging, studies have reported mixed results regarding success of SLN identification (9–11). The largest and most recent randomized controlled trial demonstrated markedly lower mapping rates for patients receiving lidocaine injections. Furthermore, some of the studies utilized special preparations of lidocaine along with the radiotracer, something not feasible for many

practices. As a result, many nuclear medicine radiologists and surgeons are uncomfortable using injectable lidocaine and instead rely on topical anesthesia for the radiotracer injection (12).

**Table. Summary of Existing Literature on SLN Mapping Rates after Lidocaine Injections**

Author	Design	Study years	Sample size	Method	SLN Mapping rates
Stojadinovic et al.	Randomized controlled trial	2006-2009	140	Prepared mixture of lidocaine and radiotracer (+/- bicarbonate) injected subareolar	
 
• 96% EMLA cream,
 
• 97% sodium bicarbonate
 
• 90% 1% lidocaine
 
• 90% 1% lidocaine + sodium bicarbonate
 

Stearns et al.	Prospective cohort with historical control	Prospective 2011-2012, historical 2005-2009	110 prospective, 187 retrospective	2cc of 1% lidocaine injected subareolar prior to radiotracer	
 
• 95% 1% lidocaine
 
• 94% historical control
 

Hawkins et al.	Randomized controlled trial	2009-2010	49	6cc of 2% buffered lidocaine injected subcutaneous	
 
• 79% control
 
• 72% 1% lidocaine + sodium bicarbonate
 

**3.3 No topical anesthetic has been proven to be superior for controlling pain associated with radiotracer injection.** Topical anesthetics such as lidocaine-prilocaine cream (EMLA) have limited benefit compared to placebo (13–16). To date, there have been no studies investigating the efficacy of anesthetic patch (e.g. 5% lidocaine) or non-pharmacologic pain management for this procedure. Thus, there is still a need to investigate a practical, effective, and broadly adoptable intervention that will reduce the distress associated with preoperative radiotracer injection in breast cancer patients.

### 3.4 Preliminary observations

*Options for topical anesthetic:* Institutionally and in the literature, EMLA cream does not appear to reduce pain with radiotracer injection (13–15). The nuclear medicine department at our institution discontinued the use of EMLA due to perceived lack of efficacy and workflow challenges associated with implementing EMLA application into practice (which may have impacted effectiveness).

The current standard of care at our institution is application of ice to the breast before radiotracer injection. Application of ice to the breast has not been directly studied in the setting of radiotracer injection, but ice and topical vapocoolant sprays have been found to reduce the pain of procedures such as venous and arterial cannulation in adults (17–20). According to breast cancer providers at our institution, patients continue to report significant pain with the procedure when ice is used as the topical anesthetic.

Lidocaine patches, in contrast to EMLA, are easier for patients and providers to apply and have demonstrated efficacy in neuropathic pain as well in aesthetic procedures (21–23). This represents a potential option for a topical anesthetic.

*Novel intervention for procedural pain:* Topical high frequency vibration combined with topical cooling is a novel method to alleviate acute procedural pain. It has been studied and implemented largely in the pediatric population. It is thought that mechanoreceptor and noxious thermal inhibitory stimulation alter normal pain conduction pathways and offers better pain control than cooling alone (24). This combined approach has been found to significantly reduce the pain and distress of venipuncture (25). This intervention is the most commonly used non-pharmacologic intervention for venipuncture pain within our institution's Children's Hospital with good anecdotal success in reducing pediatric pain. The literature in the adult population of combined vibration and cold therapy is much scarcer, but preliminary data suggests that this intervention is beneficial especially in those with greater pre-procedural anxiety and is superior to cooling alone (24). A combination of vibration and cooling has not been widely implemented in our adult population for any acute procedural pain, making it an underexplored and promising area of study. Our initial observations are that application of this type of vibration to the periareolar breast and even nipple areolar complex is tolerable.

#### **4. Study Objective and Specific Aims**

Primary Objective: To test the effectiveness of four alternative approaches to topical anesthesia on pain associated with radiotracer injection for women diagnosed with breast cancer undergoing sentinel lymph node mapping.

Secondary Objectives:

[figure not shown]
1. To assess patient satisfaction with pain control modality for radiotracer injection.
2. To identify barriers to implementation of the different pain control interventions.

#### **5. Research Design and Methods**

[figure not shown]
##### **5.1 Study Overview and Schema**

This is a randomized clinical trial testing the effectiveness of four alternative approaches to topical anesthesia for radiotracer injections for women diagnosed with breast cancer undergoing sentinel lymph node mapping. We will test two types of topical anesthetic (ice and lidocaine patch) with and without the addition of a topical high frequency vibration device (always combined with cooling). Ice is our control group as it reflects current standard of care at our institution.

##### **Patient schema**

## Nuclear Medicine Provider schema

## 5.2 Selection of Participants

Inclusion criteria:

- $\geq 18$  years of age
- biopsy proven breast cancer
- planned standard radiotracer injection (intradermal injection in the upper outer quadrant of the involved breast) for sentinel lymph node biopsy in the nuclear medicine department on the same day as surgery; standard versus non-standard injection is determined by the surgeon based on patient history at the time of procedure scheduling

Exclusion criteria:

- males
- pregnancy
- local anesthetic allergy or active use of the following medications
  - Abametapir (risk X)
  - Conivaptan (risk X)
  - Fusidic Acid (risk X)
  - Idelalisib (risk X)

- Mifepristone (risk D)
- Stiripentol (risk D)
- Amiodarone (risk C)
- Dofetilide (risk C)
- Dronedarone (risk C)
- Ibutilide (risk C)
- Sotalol (risk C)
- Vernakalant (risk C)
- Non-English speaking/reading
- Unable to provide informed consent
- Unable to participate with surveys
- Undergoing radiotracer injection the day prior to surgery or intra-operatively at the time of initial surgical scheduling
  - If patients are initially scheduled for same-day preoperative injection, complete all enrollment procedures (including randomization), and surgery is re-scheduled for a day prior to surgery or for intra-operative injection, they will be excluded if:
    - randomized to a lidocaine patch arm (Arms C or D) re-scheduled for an intra-operative injection
- Planned non-standard radiotracer injection site

### **5.3 Screening and recruitment:**

#### *Screening:*

Introduction of the study: Patients being cared for by breast surgeons within the UW Breast Center will be eligible for consideration. Clinic schedules will be reviewed in advance by the study team to screen for patients meeting eligibility criteria. Breast surgeons will identify additional eligible patients and confirm eligibility of patients identified on study team screening.

Potential participants will be informed about the study by a member of their clinical care team at a standard of care visit or during a standard care phone call. Those interested in learning more will be contacted by a member of the study team to further discuss the study.

#### *Recruitment:*

The study team will offer all interested patients a study information packet (study information sheet, consent form, and baseline Wong-Baker FACES pain rating scale). Interested patients can receive the packet via email, mail, or in-person at a UWCHC visit, according to their preference. Only study team members will provide these materials to interested patients and/or conduct in-depth discussion of the study. The study team will only email a link or electronic information packet after discussion of the inherent risks of email transmission of information and the patient has verbally consented to email receipt of this information.

Patients will be informed that final study eligibility will be determined based on the final scheduling of their surgical procedure, specifically whether the radiotracer injection is the same day as the surgery.

The study team will review the operating room schedules to identify patients undergoing standard preoperative radiotracer injection for sentinel lymph node mapping on the same day as breast surgery.

Interested patients who are fully eligible will be contacted by study team members to further discuss the study and consent. **5.4 Consent process:**

#### **5.4.1 Patient consent**

We request a waiver of signed consent and alteration of HIPAA authorization such that participant signature is not required for consent and authorization. Informed consent will be verbally obtained and documented prior to any research activities. After a patient expresses desire to enroll, informed consent will be obtained. Patients will have already received a copy of the informed consent and authorization document. If a new copy is required, this will be emailed or mailed to the patient based on their preference. If the patient will be at the hospital or clinic for another reason, they can also obtain a copy of the consent and authorization from the study team at that time. As much time as needed will be given for potential subjects to decide whether or not to participate in this study. Subjects will be informed that they are not obligated to participate in the study.

#### **Waiver of signed consent:**

The research presents no more than minimal risk of harm to subjects and involves no procedures for which written consent is normally required outside of the research context. Use of lidocaine patches and the Buzzy device for local pain control are not procedures that require written consent under non-research settings. Similarly, the surveys in this protocol present low psychological risk and would not require written consent under a non-research setting. The waiver of signed consent will not adversely affect the rights and welfare of subjects. The research cannot be practicably carried out without waiver of signed consent. Not all participants will enroll at the time of initial clinic visit. For patients who choose to enroll remotely over the phone, the short time between surgical scheduling and surgery date impedes their ability to return a signed consent before their surgery date and therefore formally enroll in the study. Subjects will be provided with a consent document to guide the informed consent process and will be given the opportunity to have all questions answered.

#### **Alteration of HIPAA Authorization:**

The use of protected health information involves no more than minimal risk to the privacy of individuals. Data privacy practices will protect identifiers from improper use and disclosure (see 11 Records to be kept, Privacy, and Confidentiality). Identifiers will be destroyed at the earliest opportunity consistent with research conduct. Participants will receive a consent and authorization document for their records detailing how protected information will not be reused or disclosed. Research cannot be practicably conducted without the alteration of HIPAA authorization. Not all participants will enroll at the time of initial clinic visit. For patients who choose to enroll remotely over the phone, the short time between surgical scheduling and surgery date impedes their ability to return a signed authorization before their surgery date and therefore formally enroll in the study. The research cannot be practicably conducted without access to and use of protected health information. Protected health information is required to access participant medical records for data elements of medical/surgical history and surgery data.

Consent can occur in one of the following ways:

- 1) In-person in the breast center: If the patient agrees to participate in the study after discussing with the breast surgeon and would like to undergo informed consent at the time of their clinic consultation, informed consent will be obtained in a closed, private room by a member of the study team at the Breast Center. A verbal consent and authorization will be obtained and documented. The patient will be given a copy of the consent form for their records. Patients will be informed that their final study eligibility will be determined after the surgery is scheduled and it is confirmed that the radiotracer injection will happen on the same day as surgery.
- 2) In-person at another location in the hospital or clinic: If the patient agrees to participate and has another appointment at the UW hospital and clinic, the study team can meet with the patient to obtain informed consent. The consent would be obtained in a closed, private location by a member of the study team. A verbal consent and authorization will be obtained and documented. The patient will be given a copy of the consent form for their records.
- 3) By telephone: The study team will review details of the study with the patient. Patient identity will be verified by verbally stated full name and date of birth. A verbal consent and authorization will be obtained and documented.

Subjects will receive a copy of the consent form and will be given contact information for study coordinator and PI for any additional questions.

### **5.5 Randomization:**

After consent for enrollment has been obtained and eligibility confirmed, patients will be randomized to one of four intervention arms. Patients will be stratified by whether or not they are scheduled to undergo a breast radiology procedure (eg. wire localization, seed localization, elucent clip) prior to nuclear medicine injection. Treatment group allocation will be communicated to nuclear medicine providers with a colored paper printout that travels with the patient on the day of surgery.

### **5.6 Study procedures:**

#### Intervention Arms

Intervention Group A (control and current standard of care)- Topical cooling: An ice pack will be applied to the upper outer quadrant of the areola/breast for 1.5 minutes immediately prior to radiotracer injection(s).

Intervention Group B- Topical cooling plus vibration distraction device application: An ice pack will be applied to the upper outer quadrant of the areola for 1.5 minutes immediately prior to radiotracer injection. For the last minute, the vibrating distraction device (Buzzy®) will be placed over the ice. The vibrating distraction device (Buzzy®) will be moved lateral at the time of the surgical prep but kept on the breast during the injection. In the event that a patient requires additional injections for adequate mapping, as determined by the image interpreting staff, the Buzzy® and ice treatment will be repeated prior to each additional injection.

Intervention Group C- lidocaine patch: A 4% lidocaine patch will be applied in the preoperative holding area to the upper outer quadrant at least 1 hour prior to radiotracer injection. Lidocaine

patches will be prescribed at the time of study enrollment. If a patient arrives for injection and does not have a lidocaine patch in place, they will be treated according to the standard of care (ice). In the event that a patient requires additional injections for adequate mapping, as determined by the image interpreting staff, the patient will receive the standard of care treatment (ice) prior to each additional injection.

Intervention Group D- lidocaine patch along with topical cooling plus vibration distraction device:

A 4% lidocaine patch will be applied in the preoperative holding area to the upper outer quadrant at least 1 hour prior to radiotracer injection. The patch will be removed and the ice pack will be applied for 1.5 minutes prior to prep. For the last minute, the vibrating distraction device (Buzzy®) will be placed over the ice. The vibrating distraction device (Buzzy®) will be moved lateral at the time of the surgical prep but kept on the breast during the injection.

Lidocaine patches will be prescribed at the time of study enrollment. If a patient arrives for injection and does not have a lidocaine patch in place, they will be treated with the Buzzy® and ice intervention prior to injection. In the event that a patient requires additional injections for adequate mapping, as determined by the image interpreting staff, the Buzzy® and ice treatment will be repeated prior to each additional injection.

Device:

Buzzy®: The Buzzy® device is IDE exempt under 21 CFR Part 812.2(c)(2) as an approved device being investigated in accordance with its labeling. Buzzy® has received FDA 510(k) clearance for pain control with injections. Buzzy® is a battery-powered device that produces high frequency vibration and is to be combined with a cooling element (e.g. ice pack) when applied to the skin for pain control. Buzzy® is thought to work by simultaneous stimulation of mechanoreceptor and noxious thermal inhibitory neurons which together modulate the transmission of pain.(26)

Drug:

Lidocaine patch 4% OTC: The patch provides 4g of lidocaine per 100g patch and is applied to the skin. This drug is exempt from IND 21 CFR Part 312.2(b)(1) as a lawfully marketed drug used in clinical investigation. This study is not intended to identify a new indication for the drug or for change in drug labeling. This investigation does not involve a route of administration or dosage level or use in a patient population or other factor that significantly increases the risks (or decreases the acceptability of the risks) associated with the use of the drug product. The dosage level used in the study is the standard dosage level of one patch of 4% lidocaine. The route of administration is the approved topical route of administration. The patient population in the study is not at increased risk from the drug related to any specific population factors.

**5.6.1 Surgical re-scheduling:**

If a participant is enrolled after meeting all eligibility criteria but the surgery is rescheduled, the participant's surgery date eligibility will be re-evaluated. If the participant is rescheduled for surgery with same-day preoperative nuclear medicine injection, then study procedures will be carried out per protocol. If the participant is rescheduled for surgery with intraoperative nuclear medicine injection, she will be withdrawn from the study as she will be unable to undergo study procedures. If the participant is rescheduled for surgery with a day-before surgery nuclear medicine injection she will undergo study procedures only if she was originally randomized to either the ice (arm A) or the ice + buzzy (Arm B) arms. If the participant is rescheduled for

surgery with a day-before surgery nuclear medicine injection she will be withdrawn from the study if she was originally randomized to either the lidocaine patch (arm C) or the lidocaine patch + ice + buzzy (Arm D) arms as lidocaine patches cannot be administered the day before surgery for logistical reasons.

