## 8. Statistical Considerations

### 8.1 Analysis

Data will be analyzed with intervention arms masked. All scales will be constructed in a manner consistent with scale development, including item non-response. We will compare mean post-procedural pain scores (primary outcome) and other continuous secondary outcomes with ANOVA, testing the null hypothesis that mean post-procedural pain scores will not statistically differ between the control and intervention arms. Pairwise differences between each of the intervention arms and the control arm will be assessed with t-tests. Differences in potential control measures between patients randomized to the control and intervention arms that arise by chance will be examined using a chi-square test or Fisher's exact test for categorical variables and analysis of variance (ANOVA) or Kruskal-Wallis test for continuous variables (depending on distribution), respectively. Should there be significant differences in control measures between arms, an analysis of covariance (ANCOVA) will be used to assess the primary outcome, including significant covariates. Differences in the secondary dichotomous measures (sentinel lymph node mapping, patient recommendation) will be assessed with Chi-Square analysis. We will summarize responses to open ended questions in the patient survey and adherence to intervention. All analyses will follow an intention to treat approach. We will summarize the responses from the nuclear medicine providers/staff to determine what arm was perceived to be the most effective method for pain control and the easiest to administer.

Secondary analysis will be performed on the type of radiotracer received and pain scores.

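### Patients moved to a day-before injection after randomization stay in Arms A and B but are withdrawn from C and D, and the intention-to-treat statement does not cover this

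*Combined protocol and SAP*

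**What the plan says.** Section 5.6.1 sets the rules for patients whose surgery is rescheduled after enrolment.

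- Day-before injection, Arms A and B: the patient continues; "she will undergo study procedures only if she was originally randomized to either the ice (arm A") or to Arm B.
- Day-before injection, Arms C and D: "she will be withdrawn from the study if she was originally randomized to either the lidocaine patch (arm C") or to Arm D. The reason given is logistical: patches cannot be provided the day before surgery.
- Intra-operative injection, any arm: "If the participant is rescheduled for surgery with intraoperative nuclear medicine injection, she will be withdrawn from the study".

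Section 5.5 places randomization before these events: "After consent for enrollment has been obtained and eligibility confirmed, patients will be randomized to one of four intervention arms". Section 8.1 plans an ANOVA over the arms and t-tests of each intervention arm against Arm A. Its only statement on the analysis population is "All analyses will follow an intention to treat approach".

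**The concern.** The day-before rule acts after randomization and depends on the assigned arm. Day-before pain scores can enter the A and B means but never the C and D means. The intra-operative rule in 5.6.1 is the same for every arm and raises no such problem.

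The comparisons that cross the two rules are A-vs-C, A-vs-D and the omnibus ANOVA. A-vs-B follows one rule throughout. If pain differs by day of injection, part of any observed difference between the ice arm and a patch arm would reflect who was kept, not the treatment.

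The intention-to-treat sentence does not settle this. Withdrawn C and D patients will have no post-injection score, so an analysis of all randomized patients cannot be carried out as labelled, and the plan does not say what replaces it. Day of injection is neither a stratification factor (5.5) nor a named chart-review item (5.7.1), although that list is open-ended.

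**Working it through.** **Inputs from section 8.2:** control mean 6.0, SD 2.6 in all arms, alpha 0.05, 40 analyzed per arm, 2-point target difference, 180 enrolled (45 per arm) for 160 analyzed.

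**Inputs assumed, because the documents give neither:** the share r of randomized patients moved to a day-before injection, 5–10% (2.25–4.5 of 45 per arm); and the difference d in mean pain, day-before minus same-day, 1–2 points in size and of either sign. A d of 2 is a high end, since it equals the protocol's whole clinically significant difference.

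**The plan's own figure.** For a four-arm ANOVA, λ = Σ n(μᵢ − μ̄)²/σ². The middle arm means are not stated. With evenly spaced means 6, 5⅓, 4⅔, 4, λ = 40 × (1 + 1/9 + 1/9 + 1)/6.76 = 13.15, which gives 86.6% power, close to the stated 85%.

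**Bias.** With no treatment effect and rescheduling unrelated to arm, the retained mean is μ + r·d in A and B and μ in C and D. The A-vs-C and A-vs-D contrasts are therefore biased by r·d:

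- smallest: 0.05 × 1 = 0.05 points (2.5% of the 2-point target)
- largest: 0.10 × 2 = 0.20 points (10% of the target)

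**Type I error, 40 per arm.** Pairwise noncentrality is r·d/(2.6 × √(2/40)) = r·d/0.581. For the omnibus test A and B are both shifted, so λ = 160 × (r·d/2)²/6.76. At a bias of 0.20 these are 0.344 and 0.237.

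| Bias (points) | Pairwise | Omnibus |
|---|---|---|
| 0.05 | 5.1% | 5.1% |
| 0.10 | 5.3% | 5.3% |
| 0.20 | 6.3% | 6.4% |

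**Type I error on the enrolment base** (A and B 45; C and D 45 × (1 − r)):

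| r × d | C, D per arm | Pairwise | Omnibus |
|---|---|---|---|
| 5% × 1 | 42.75 | 5.1% | 5.1% |
| 5% × 2 | 42.75 | 5.4% | 5.4% |
| 10% × 1 | 40.5 | 5.4% | 5.4% |
| 10% × 2 | 40.5 | 6.4% | 6.5% |

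A simulation that mixed day-before and same-day patients in Arm A (200,000 runs, 45 vs 40, 10% × 2) also gave 6.4%.

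**Power at 2 points: current rule against one same-day rule in all arms** (evenly spaced means for the omnibus test):

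| Base, r | Pairwise, current → one rule | Omnibus, current → one rule |
|---|---|---|
| 45, 5% | 94.5% → 94.0% | 89.8% → 89.0% |
| 45, 10% | 93.9% → 92.8% | 88.9% → 87.0% |
| 40, 5% | 91.8% → 91.1% | 85.6% → 84.6% |
| 40, 10% | 91.1% → 89.6% | 84.5% → 82.3% |

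The 40-per-arm rows take rescheduling losses off the final target and so are the pessimistic case; 8.2 already allows 180 to fall to 160.

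**The case against.** **The effect may be negligible.** Several provisions limit how many patients can be moved. Section 5.3 says "final study eligibility will be determined based on the final scheduling of their surgical procedure", randomization follows confirmed eligibility, and 5.4.1 refers to "the short time between surgical scheduling and surgery date". Nothing in the documents shows that pain differs by day of injection; if it does not, the bias is zero. Error above 6% appears only in the 10% × 2-point case. All of this stands, and it is why the bias is called modest.

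**The plan can be read as complete for A and B.** Taking 5.6.1 and 8.1 together, day-before A and B scores would be analyzed in their assigned arms. That is a fair reading, but it confirms the asymmetry: those scores count in two arms and cannot exist in the other two.

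**Section 5.2 may state a different rule.** As printed, its rescheduling sub-bullet excludes only patch-arm patients moved to intra-operative injection and names no day-before exclusion. The concern therefore rests on 5.6.1 as written. The sub-bullet may have lost text in extraction; the two sections need checking against each other.

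**A same-day set conditions on a post-randomization event and drops observed scores.** This is true, and a same-day sensitivity analysis beside the current primary analysis would be a lighter change. But with no day-before scores in C and D, same-day patients in all arms are the only like-for-like comparison available, so that set is the better primary. Its assumption must be stated.

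**Conclusion.** The concern holds. Under 5.6.1, retention after randomization depends on the arm, and 8.1 names an approach that cannot be met for withdrawn C and D patients. That much is certain from the text.

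The size is uncertain. Over the assumed range the bias is 0.05–0.20 points in either direction and type I error is 5.1–6.5%. It is zero if nobody is moved or if pain does not differ by day. It would matter more only if rescheduling were common: at 20% and 2 points (40 in A, 32 in C) the bias is 0.40 points, with error of 9.8% pairwise and 10.3% omnibus. The plan should be corrected because the inconsistency is clear and the remedy is cheap, not because a large distortion is expected.

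**What to change.** In section 8.1:

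1. Define the primary comparison set by one rule for all four arms: randomized patients whose injection was given pre-operatively on the day of surgery, analyzed as randomized. Call it modified intention to treat.
2. Add a sensitivity analysis that includes the day-before A and B scores.
3. State that the set is unbiased only if rescheduling does not depend on the assigned arm. This cannot be taken for granted: "Lidocaine patches will be prescribed at the time of study enrollment" (5.6), so the arm can be known before a date is changed.
4. Report rescheduling and withdrawals by arm and reason.

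In 5.7.1, name day of injection as a recorded item. Separately, check the rescheduling sub-bullet in 5.2 against 5.6.1 and reconcile them if they differ; this review takes no position on which should stand.

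The cost is wording, one data item and the loss of day-before A and B patients from the primary analysis. Against the current rule, pairwise power falls by 0.5 or 1.2 percentage points (5% or 10% rescheduled from 45 per arm), or by 0.7 or 1.5 points if losses come off 40 per arm. Omnibus power falls by at most 2.2 points (84.5% to 82.3%).
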